**SURveillance of PREMalignant stomach –
individualized Endoscopic follow-up**

The SUPREME Project

04th June 2020
CES 194/020 (IRB approval)

SUMMARY

Introduction: Gastric atrophy and intestinal metaplasia are the principal precursors for gastric cancer and, therefore, are considered gastric premalignant conditions. Although current guidelines recommend surveillance of individuals with these conditions, the best method for its identification and staging (histological vs endoscopy) and the best time schedule for follow-up are still controversial. **Aims:** To describe for the first-time patients with premalignant conditions both clinically (familial history), histologically (OLGA/OLGIM; complete/incomplete metaplasia) and endoscopically (EGGIM) using validated scales and to describe evolution of these parameters through time. To estimate prospectively the gastric cancer risk according to EGGIM stages. To define the best endoscopic surveillance follow-up for the several stages considering clinical, histological and endoscopic factors. **Methods:** Multicenter study involving different gastroenterology departments from several countries. Consecutive patients older than 45 years scheduled for upper endoscopy in each of these centers will be evaluated by High-Resolution-endoscopy with virtual chromoendoscopy and EGGIM will be calculated. Guided biopsies (if areas suspicious of IM) and/or random biopsies (if no areas suspicious of IM) in antrum and corpus will be made and OLGA/OLGIM stages calculated. Patients will be evaluated in clinical consultation and database will be fulfilled. All patients will be eradicated for *Helicobacter pylori* infection if positive. At that occasion, all the patients with EGGIM \geq 5 and/or OLGA III/IV and/or OLGIM III/IV will be randomized for yearly (12 to 16 months) or every three years (32-40 months) endoscopic follow-up during a period of 6 years (SUPREME I). Endoscopic observational follow-up will be scheduled for patients with EGGIM 1-4 and OLGIM I/II at 3 and 6 years (SUPREME II). For individuals with no evidence of IM (EGGIM 0 and OLGIM 0, OLGA 0-II) a follow-up endoscopy 6 years after will be proposed (SUPREME III). **Expected results:** This study will help us to define which clinical factors influence gastric cancer risk and which is the best way to determine advance gastric premalignant conditions (histology or endoscopy or both). Moreover, a precise incidence rate of dysplasia/neoplasia among patients with gastric preneoplastic conditions will be established and an individualized endoscopy follow-up for these patients may be reached. Furthermore, an improvement of the definitions and current guidelines can be expected.

INTRODUCTION

Gastric cancer (GC) is still a major problem in the world, being ranked 5th in incidence and 3rd in cancer-related mortality worldwide ¹. Intestinal-type gastric adenocarcinoma represents the final outcome of the inflammation–atrophy–metaplasia–dysplasia–carcinoma sequence, known as the Correa cascade ²⁻⁶. *Helicobacter pylori* (Hp) is considered the initiator of this cascade, however, less than 1% of the patients infected develop cancer. Nevertheless, almost 1/3 of the infected patients will develop chronic atrophic gastritis and intestinal metaplasia (IM), that are considered precancerous conditions because they confer by themselves a risk for the development of gastric cancer and constitute the background in which dysplasia and adenocarcinoma may occur ^{3, 7-9}.

Advanced stages of atrophic gastritis meaning significant atrophy or IM (as the best and more reliable marker of atrophy) particularly if affecting both antral and corpus mucosa are considered the main risk factors for cancer (as opposed to initial stages of gastritis). However, even though diverse efforts were made to stage or classify individuals according to the severity and/or extension of these changes the best method for risk stratification is still controversial. Endoscopic biopsies of antrum and corpus appear to be the best method for staging of gastritis. The OLGA (Operative Link for Gastritis Assessment), or OLGIM (Operative Link for Gastritis assessment based on Intestinal Metaplasia) systems have been proposed for staging of atrophy and IM, respectively, and showed to be good predictors of gastric cancer risk. Since the staging of atrophy needs the grading of the severity of gland loss and this presents a poor inter- and intra-observer agreement, OLGIM appears to be better whenever staging of mucosal changes is aimed ¹⁰⁻¹⁵. The problem with these histological grading systems is that atrophic changes of the mucosa may be unevenly distributed throughout the mucosa meaning that 1) important changes may be missed by random biopsies and 2) in different time evaluations the grading may be different only because biopsies were done in different places of the mucosa.

With this in mind in theory an endoscopic evaluation will be better for a correct staging of gastritis/preneoplastic conditions by seeing all the mucosa (not depending only in small fragments of the mucosa). Nevertheless, classically the yield of conventional endoscopy to stage gastritis was suboptimal what compromised endoscopy without biopsies as a valid method for gastritis staging. Our group created a classification of endoscopic features with high-resolution and virtual chromoendoscopy that showed to be reliable and accurate for the diagnosis of IM and dysplasia/cancer ¹⁶. Moreover, we created a scale for

Endoscopic Grading of Gastric Intestinal Metaplasia (EGGIM) that showed strong correlation with OLGIM stages and that we recently validated in multicenter study. We have also shown retrospectively that EGGIM staging was associated to gastric cancer risk and to the risk of new lesions after endoscopic resection of early gastric cancer ^{17, 18}.

Clinical factors like family history, smoking and alcohol, may also influence gastric cancer risk but they rarely were evaluated prospectively.

Recognizing the importance of family history but more importantly of atrophic gastritis in the development of gastric cancer, current guidelines recommend endoscopic follow-up of patients with these conditions, even though the timing for endoscopic evaluation relies in scarce evidence and mostly based in expert opinion.

We believe that this project can help to improve the estimates of current guidelines and potentially redefine the "gold-standard" of 'a at risk profile' for gastric cancer.

AIMS

Primary aims:

1. To estimate prospectively which is the incidence rate for dysplasia/cancer among individuals with different stages of gastric precancerous conditions defined both endoscopically and histologically;
2. To define the best endoscopic follow-up for the different patients with gastric precancerous conditions considering clinical, endoscopic and histological aspects.

Secondary aims:

1. To establish prospectively for the first time the dysplasia/gastric cancer risk among the different EGGIM stages;
2. To define different groups of patients with premalignant gastric conditions based on endoscopy and histology simultaneously;
3. To evaluate the progression/regression of gastritis through time, for the first time considering both endoscopy and histology;
4. To define the need of random biopsies in patients under surveillance because of gastric premalignant conditions (based on the prevalence of dysplasia without endoscopic features suggestive of that);
5. To determine the effect of *H. pylori* eradication in endoscopic and histological staging.

METHODS

Setting and study design

- A **Prospective randomized multicenter trial**;
- Centers:
 1. International gastroenterology departments Europe and America
 - Access to HR-scopes with virtual chromoendoscopy (NBI, BLI or iscan);
 - Endoscopists must be experienced in virtual CE diagnosis (at least 100 previous virtual CE procedures/diagnosis in the stomach);
 - Participation granted if at least 100 patients per center complete the protocol, 25 of these in the randomization arm (2 authors per 50 patients, maximum of 6 authors per center);
 2. Confirmed centers (n=15) per country:
 - Portugal:
 - Portuguese Oncology Institute of Porto
 - Portuguese Oncology Institute of Coimbra
 - Porto University Hospital Centre
 - Vila Nova de Gaia and Espinho Hospital Centre
 - Braga Hospital
 - Guimarães Hospital
 - Beatriz Ângelo Loures Hospital
 - Spain:
 - Navarra Hospital
 - France:
 - University Hospital of Nantes
 - Italy
 - Sant' Andrea University Hospital
 - Romania
 - Mures Hospital
 - Poland
 - Centre of Oncology Institute Warsaw
 - England

- Nottingham University Hospitals
- Brasil
 - University Hospital of Minas Gerais
- USA
 - Los Angeles Hospital

Initial patients' selection

- Individuals **older than 45 years old** scheduled for upper GI endoscopy with indication for gastric biopsies (clinical or endoscopic findings), including those with known gastric pathology (e.g. auto-immune gastritis) or premalignant conditions (e.g patients under surveillance because of atrophic gastritis);
- **Exclusion criteria (1st phase, clinical):** History of previous gastrectomy; History of endoscopic resection of neoplastic lesion; history of previous gastric dysplasia (even with no detectable lesion); hereditary syndromes that increase gastric cancer risk (PAF; Lynch); serious comorbidities (ASA 3 or more); medication with anticoagulants.

Endoscopic and biopsies protocol

- In all patient's complete gastroscopy first with White light and then with virtual CE will be made; all ESGE major quality parameters (including time) will be recorded;
- EGGIM will be calculated according to what previous described ^{17 18};
- If EGGIM 0 (no endoscopically apparent IM) biopsies will be made in antrum, incisura and corpus according to Sydney-Houston protocol (at least two fragments antrum and corpus and one in the incisura);
- If $EGGIM \geq 1$ guided biopsies of suspicious areas of IM should be made replacing the random biopsies in that particular area (e.g. if IM in lower curvature but not in the greater curvature of the antrum then you should do targeted biopsies in the lower curvature and random in the greater curvature; if IM in both antrum areas then you should only do targeted biopsies; in each case at least two antrum fragments should be taken and biopsies should be sent in the same antrum vial);
- Antrum, incisura and corpus fragments should be sent in 3 separate vials;

- **Exclusion criteria (2nd phase, endoscopic):** upper GI tract neoplasia; hemorrhagic gastritis; upper GI tract varices; suspicious area of gastric superficial lesion/dysplasia; impossibility to complete biopsy protocol; **not exclusion criteria:** *benign gastric ulcer, gastric erosions, papules or polyps (in these cases gastric biopsies/resection of these areas should be sent in separate vials); esophagitis; duodenal erosions or ulcers.*

Patient inclusion in the surveillance trial and randomization

- All patients that complete the endoscopy and biopsy protocol will be evaluated 2 to 6 weeks after in a clinical consultation.
- To all patients with Hp infection, eradication will be offered and confirmed by non-invasive methods.
- Patients with EGGIM ≥ 5 or OLGA/OLGIM III/IV (**pre-malignant stomach group – SUPREME I**) will be randomized to endoscopic surveillance every one (12 to 16 months) or three years (32-40 months);
- Patients with EGGIM 1-4 (and not higher) and/or OLGIM I/II (and not higher) and OLGA stage not higher than II will be proposed for endoscopy at 3 and 6 years (**initial atrophic gastritis group – SUPREME II**);
- Patients with EGGIM 0 and OLGA 0/I/II; and patients with EGGIM 1-3 with biopsies negative for IM (OLGIM 0) and OLGA not higher than II will be proposed for endoscopy at 6 years (**non-pre-malignant stomach group – SUPREME III**).
- All patients will be included in the surveillance trial and clinical, endoscopic and histologic data (including type of IM) will be fulfilled on an online database (see attachment with all the variables being considered);
- Randomization to the different arms in the pre-malignant stomach group will be made by the computer software after all the variables have been fulfilled:

Subsequent Endoscopic and biopsies follow-up

- In all patient's complete gastroscopy first with White light and then with virtual CE will be made;
- Suspicious lesion with dysplasia/cancer will be biopsied 1-2 fragments in a different vial; if an irregular area of mucosa (pattern C) with no clearly defined lesion then 1-2 guided biopsies fragments will be taken and sent in a different vial;

- EGGIM will be calculated according to what previous described ^{17 18};
- If EGGIM 0 (no endoscopically apparent IM) biopsies will be made in antrum, incisura and corpus according to Sydney-Houston protocol;
- If EGGIM 1 or more guided biopsies of suspicious areas of IM should be made replacing the random biopsies in that particular area (e.g. if IM in lower curvature but not in the greater curvature of the antrum then you should do targeted biopsies in the lower curvature and random in the greater curvature; if IM in both antrum areas then you should only do targeted biopsies; in each case at least two antrum fragments should be taken and biopsies should be sent in the same antrum vial);
- Antrum, incisura and corpus fragments should be sent in 3 separate vials;

Subsequent clinical evaluation and follow-up

- All patients that complete 2nd endoscopy and biopsy protocol will be evaluated 2 to 6 weeks after in a clinical consultation.
- Endoscopic and histologic data of the second/third procedure will be fulfilled on an online database.
- If no lesion and no irregular area were seen and random biopsies do not present dysplasia then the patient maintain the previous defined endoscopic follow-up (1 or 3 years).
- If an irregular area was seen (with no clearly defined lesion) but guided biopsies negative for atypia/dysplasia then the patient maintain the previous defined endoscopic follow-up (1 or 3 years).
- If an irregular area was seen (with no clearly defined lesion) and guided biopsies present atypia/dysplasia or if random biopsies of any gastric area present dysplasia then outcome 1 was reached and patient follow-up should respect current guidelines (endoscopy 3-6 months if high-grade and 6-12 months if low-grade dysplasia) ¹⁹.
- If a suspicious superficial lesion was seen and biopsies present atypia, dysplasia or cancer then staging and resection of the lesion will be made; Only after resection and/or complete staging, the outcome will be assumed according to the following:
 1. Outcome 1: lesion presenting only dysplasia (low or high grade)
 2. Outcome 2: lesion presenting carcinoma

- Outcome 2.1 intramucosal carcinoma with low-risk criteria (“curative” criteria)
- Outcome 2.2 submucosal, diffuse type or intramucosal carcinoma with high-risk criteria (“non-curative” criteria)
- Outcome 2.3: advanced cancer (more than previous, implying impossibility of endoscopic resection)

End of study

- The study is designed for 6 years, when all data will be analyzed and results presented;
- Patient follow-up will be completed at 6 years or when one of the outcomes is reached;
- Continuation of the study after 6 years is possible and predictable and will be decided after data analysis.

Subprojects

[figure not shown]
- In order to clarify the natural history of other specific situations not considered in the main project two additional groups of patients will be followed-up prospectively:
 1. Patients with persistent Hp gastritis and non-premalignant stomach (Patients with EGGIM 0 and OLGA 0/I/II; and patients with EGGIM 1-3 with biopsies negative for IM (OLGIM 0) and OLGA not higher than II);
 - We suggest endoscopic follow-up in 3 (if family history of gastric cancer) to 6 years (if no family history of gastric cancer) in these group of patients;
 - We predict 12 years follow-up of these patients (two to four follow-up endoscopies);
 - Data analysis after 12 years follow-up;
 2. Patients that in follow-up reach outcome 1 (dysplasia) but with no clearly defined lesion for resection (small irregular areas with dysplasia) or random biopsies with dysplasia; Natural history of these patients is not clearly defined since in previous studies many of them might already present a lesion at the time of diagnosis.

- We suggest endoscopic follow-up accordingly to guidelines, 3-6 months if high-grade dysplasia and 6-12 months if low-grade dysplasia;
 - If after two negative endoscopies with no dysplasia/lesion, then we suggest endoscopy in 1 (if family history) to 3 years (if no family history).
- In both of these subprojects the endoscopic and biopsies protocol will be the same of the main project.

Sample size calculation (SUPREME I)

- We predict that the shorter interval of follow-up (1 year) will allow the diagnosis of lesions in a less advanced stage (more outcome 1 – dysplasia - and lower or inexistent outcome 2 - cancer);
- We anticipate that 1% of patients at risk per year will develop one of the outcomes (6% at the end of the 6-year follow-up) and that most of outcomes 2 (cancer) will be reached in the longer period of follow-up (3 year) for a 6-year total of 1% outcome 2 in the 1-year follow-up group (and 5% outcome 1) and 5% in the 3-year follow-up group (and 1% outcome 1);
- For showing this 4% incidence difference between the two groups (4% more incidence of outcome 2 in the 3-year follow-up group) at the end of follow-up (6 years) with an alpha level of 0.05 and a power of 90% we calculate that at least 760 patients will have to be randomized (380 per group of follow-up);
- Predicting 20% of lost to follow-up and/or necessity to anticipate endoscopy in some patients (because of symptoms/clinical reasons) we calculate that additional 152 patients will have to be randomized for a **total of 912 patients (456 per group of follow-up)**;
- We predict participation of at least 15 centers and, so, **each center must include at least 62 patients in the randomization**;
- Since inclusion of the patients in the randomization trial will only be known after an initial endoscopic and histologic evaluation, and predicting that only 20-25% of the patients will have criteria for inclusion in SUPREME I **each center must include at least 300 patients in the study (these patients will be included in SUPREME II and III)**.

Flowchart (SUPREME I, II AND III)

DISCUSSION/EXPECTED RESULTS

This prospective study will be the first study to investigate the natural history of gastric premalignant conditions in this new age of HR imaging, so based not only on random biopsies (as it was described before) but based simultaneously in HR endoscopy/chromoendoscopy and guided biopsies/histology. It has the potential to completely redefine the natural history of this disease. Moreover, it can help us to define which clinical factors influence most gastric cancer risk and which is the best way to determine and stage advance gastric premalignant conditions (histology or endoscopy or both). Moreover, a precise incidence rate of dysplasia among patients with gastric preneoplastic conditions/lesions will be established and an individualized endoscopy follow-up for these patients may be reached. Furthermore, an improvement of the definitions and current guidelines can be expected.

REFERENCES

2. Correa P. Human gastric carcinogenesis: a multistep and multifactorial process-First American Cancer Society Award Lecture on Cancer Epidemiology and Prevention. *Cancer Res* 1992;52:6735-40.
3. Kapadia CR. Gastric Atrophy, Metaplasia and Dysplasia. A Clinical Perspective. *J Clin Gastroenterol* 2003;36:S29-36.
6. Ormiston MC, W. GM, Codling BW. Five Year Follow-Up Study of Gastritis. *J Clin Pathol* 1982;35:757-60.
7. Laurèn P. The Two Histological Main Types of Gastric Carcinoma: Diffuse and So-Called Intestinal-Type Carcinoma. *Acta Pathol Microbiol Scand* 1965;64:31-49.
9. Genta RM. Review Article: Gastric Atrophy and Atrophic Gastritis - Nebulous Concepts In Search of a Definition. *Aliment Pharmacol Ther* 1998;12:17-23.

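### Where IM is visible, OLGA/OLGIM is always endoscopy-guided, so histology alone cannot be ranked against endoscopy and part of its change over time follows the endoscopic reading

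*Protocol*

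**What the plan says.** The Protocol's *Endoscopic and biopsies protocol* has EGGIM calculated during the examination and then lets it decide how tissue is taken.

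- No visible IM: "If EGGIM 0 (no endoscopically apparent IM) biopsies will be made in antrum, incisura and corpus according to Sydney-Houston protocol", that is, mapping biopsies without guidance.
- Visible IM: "guided biopsies of suspicious areas of IM should be made replacing the random biopsies in that particular area". The rule works area by area. With IM on one antral curvature only, "you should do targeted biopsies in the lower curvature and random in the greater curvature"; otherwise, "if IM in both antrum areas then you should only do targeted biopsies".
- Handling: for the antrum, "biopsies should be sent in the same antrum vial". Antrum, incisura and corpus have one vial each, and no separate labelling of targeted and random fragments is described.

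*Subsequent Endoscopic and biopsies follow-up* applies the rule again to the new reading: "If EGGIM 1 or more guided biopsies of suspicious areas of IM should be made replacing the random biopsies in that particular area".

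Two uses of the resulting stages matter here. The Summary, under expected results, says the study will help to define "which is the best way to determine advance gastric premalignant conditions (histology or endoscopy or both"), and the Discussion repeats this. Secondary aim 3 is "To evaluate the progression/regression of gastritis through time, for the first time considering both endoscopy and histology", and secondary aim 5 asks for the effect of *H. pylori* eradication on both kinds of staging.

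**The concern.** The two staging systems are not measured independently. In an area with visible IM, the pathologist receives tissue that the endoscopist chose because it looked metaplastic. Histology there is already partly the combined method, so a reported ranking of histology, endoscopy and both would not have the first option as readers understand it.

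Over time the link works through the switch of method. An area newly read as positive moves from random to targeted fragments, and an area newly read as negative moves back. If targeted fragments are more often positive, histological stage can move in the same direction as EGGIM with no change in the mucosa. For aim 5, an endoscopic reading that improves after eradication returns areas to random sampling, which by itself tends to produce apparent histological regression.

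At stake is a conclusion that histology independently confirms an endoscopic change, in a project that hopes to improve guidelines and redefine the reference standard for an at-risk profile.

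**Working it through.** **Plan's own figure.** The only computed design figure is the SUPREME I sample size. It does not bear on this point, and the documents give no fragment yields. The check is therefore a reading of the rules, plus an illustration on stated assumptions.

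**Step 1. What each rule leaves observable.**

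| Area at a visit | Fragments taken | Histology without endoscopic guidance observed? |
|---|---|---|
| IM not visible | random | yes |
| IM visible | targeted, in place of random | no |
| Antrum, IM on one curvature | one targeted, one random area, same vial | not separable as described |

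EGGIM itself does not depend on the biopsies. Three predictors of dysplasia or cancer are therefore available: EGGIM, guided OLGA/OLGIM, and both. The missing one is OLGA/OLGIM from random biopsies in patients with visible IM.

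**Step 2. When the method switches.** It switches in an area only when visible IM appears or disappears there. A change of extent within an area that stays positive leaves sampling targeted.

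**Step 3. How far positivity could move in one region.** Assume IM covers a fraction f of a region and two random fragments are taken. The chance that at least one hits IM is 1 − (1 − f)²:

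- f = 0.1: 1 − 0.81 = 0.19
- f = 0.2: 1 − 0.64 = 0.36
- f = 0.3: 1 − 0.49 = 0.51

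Against an assumed targeted yield of 0.80 to 0.95, a switch of method could move the chance of a positive region from 19–51% to 80–95%, or back, with unchanged mucosa.

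**Step 4. Induced link between the two changes.** Assumptions, none from the documents: four areas, one fragment each, two visits, no true change. IM is seen in an area with probability s, independently at each visit. A targeted fragment is positive with probability t = 0.9 and a random one with probability r. Overall positivity is p = s·t + (1 − s)·r. The correlation between change in areas seen and change in areas histologically positive is then

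√[s(1 − s)] · (t − r) / √[p(1 − p)].

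- s = 0.5, r = 0.2: p = 0.55, and 0.5 × 0.7 / √0.2475 = 0.70
- s = 0.9, r = 0.6: p = 0.87, and 0.3 × 0.3 / √0.1131 = 0.27

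A simulation of 200,000 patients per setting agrees. Each cell gives the correlation, then the mean change in histologically positive areas among patients with fewer areas seen at the second visit:

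| s | r = 0.2 | r = 0.4 | r = 0.6 |
|---|---|---|---|
| 0.5 | 0.70; −1.05 | 0.52; −0.75 | 0.35; −0.45 |
| 0.7 | 0.69; −0.99 | 0.53; −0.71 | 0.35; −0.43 |
| 0.9 | 0.56; −0.81 | 0.42; −0.57 | 0.27; −0.35 |

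With random fragments only, both quantities were about 0 in the same runs. The sign follows from t > r alone; the size depends on s, t and r.

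**The case against.** The strongest reply is that guided sampling is deliberate. The Introduction faults random biopsies because they can miss uneven changes and because grade can differ merely through a different biopsy site. The Discussion presents the study as resting on high-resolution endoscopy and guided histology together. No numbered aim ranks unguided histology against endoscopy. Random-only sampling would bring back the fault the Introduction describes. All of this stands, and nothing here argues against guided biopsies. It does not rescue the wording on histology, endoscopy or both, which the Summary and Discussion state without saying that the histology is guided.

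A reader might infer more than the documents support:

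- **That the comparison cannot be answered at all.** It can be, for EGGIM, guided OLGA/OLGIM and their combination. Discordance also remains visible: random fragments are kept where no IM is seen, and the inclusion rules provide for EGGIM 1–3 with OLGIM 0.
- **That sampling changes with any change in EGGIM.** Step 2 shows it does not.
- **That the figures above estimate the bias.** They concern fragment positivity, not OLGA/OLGIM stage, and the documents do not say how often visibility flips over unchanged mucosa.
- **That the main change analysis should use only regions sampled the same way twice.** This would drop regions where visible IM truly appeared or regressed. For aim 5 it would also condition on a post-baseline variable that eradication may affect.

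It can also be said that the analysis of change belongs in a SAP, which is not shown. That is fair for the choice of model. The sampling rule and the promised comparison, however, are fixed in the protocol, and no later analysis can supply the unguided histology.

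**Conclusion.** The point holds in limited form. In areas with visible IM, OLGA/OLGIM is endoscopy-guided at every visit. Stand-alone random-biopsy histology therefore cannot be ranked against endoscopy, and EGGIM–OLGIM agreement will tend to be higher than with independently sampled tissue. Under secondary aims 3 and 5, part of the histological change is tied to the change in endoscopic reading.

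The direction rests on one assumption: a targeted fragment is more likely to show IM than a random one. The protocol's own reason for guiding biopsies implies this. The size is unknown from the documents; the 0.27 to 0.70 range only shows that the link need not be negligible. The randomised comparison of surveillance intervals is not affected: its outcomes are dysplasia and cancer, and both arms follow the same biopsy rule.

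**What to change.** 1. In the Summary (expected results) and the Discussion, restate the question as EGGIM alone versus EGGIM-guided OLGA/OLGIM versus both. Do not claim a ranking of histology alone against endoscopy, and do not present histological change as independent confirmation of endoscopic change.
2. For secondary aims 3 and 5, keep all regions in the main change analysis. Add a supporting analysis by sampling pattern per vial at the two visits (all random, mixed or all targeted; same or switched). State with it that the same-pattern subset selects endoscopically stable regions and may understate true change.

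The cost is a narrower claim and one extra analysis. That analysis needs EGGIM findings recorded per area; the attachment listing the database variables is not in the text at hand, so this should be confirmed. No extra biopsies are needed.

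### The protocol gives no route to cancers in randomised patients who stop attending endoscopy, so the 6-year cancer comparison is open to bias of unknown direction

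*Protocol*

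**What the plan says.** All references are to the protocol.

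- *Patient inclusion in the surveillance trial and randomization*: eligible patients "will be randomized to endoscopic surveillance every one (12 to 16 months) or three years (32-40 months"). Baseline data entry covers clinical, endoscopic and histologic data and refers to an attached list of variables, which is not shown.
- *Subsequent clinical evaluation and follow-up*: the consultation is tied to a completed endoscopy: "All patients that complete 2nd endoscopy and biopsy protocol will be evaluated 2 to 6 weeks after in a clinical consultation". The one sentence on follow-up data entry is "Endoscopic and histologic data of the second/third procedure will be fulfilled on an online database".
- The same section makes outcome 1 or 2 depend on endoscopic findings and biopsies, then on resection or staging: "If a suspicious superficial lesion was seen and biopsies present atypia, dysplasia or cancer then staging and resection of the lesion will be made".
- *End of study*: "Patient follow-up will be completed at 6 years or when one of the outcomes is reached". Nothing is said about patients who stop attending before then.
- *Sample size calculation (SUPREME I)*: the powered contrast is "for a 6-year total of 1% outcome 2 in the 1-year follow-up group (and 5% outcome 1) and 5% in the 3-year follow-up group". One 20% allowance, not split by arm, covers both losses and endoscopies brought forward for symptoms or clinical reasons. It is met by 152 extra patients, giving 912 (456 per group).

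**The concern.** The powered quantity is a cumulative cancer total at 6 years in everyone randomised, but the described capture depends on attendance. A cancer that presents clinically in someone who has dropped out of surveillance is an event this trial needs to count, and no described step would record it. The schedules also differ in how often a patient is seen, so attendance and ascertainment may differ by arm.

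Few cancers are expected, about 4 or 5 against 23, so a handful of missed cases can move the result. This has to be settled while the trial runs. An analysis plan can say how lost patients are handled, but it cannot recover cancers that were never recorded.

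**Working it through.** **Inputs from the protocol.** Outcome 2 of 1% (yearly arm) and 5% (3-year arm) at 6 years; alpha 0.05; power 90%; 380 per arm, raised to 456; a single 20% allowance. Loss by arm and its timing are not given, so they are assumed below. Because the 20% also covers endoscopies brought forward, it is an upper value for loss.

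**1. The plan's own figure.** Two-sided test, pooled variance, mean proportion 0.03:

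n = [1.96 × √(2 × 0.03 × 0.97) + 1.2816 × √(0.01 × 0.99 + 0.05 × 0.95)]² / 0.04² = (0.4729 + 0.3070)² / 0.0016 ≈ 380.1, or 381 rounded up.

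This agrees with the stated 380. Then 760 × 1.2 = 912. Expected cancers at 456 per arm are 456 × 0.01 = 4.56 and 456 × 0.05 = 22.8.

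**2. Effect of the schedule alone.** Assume equal 20% dropout in both arms, uniform over 6 years, with cancers spread evenly over the scheduled endoscopies. A cancer due to be found at year v is missed with probability 0.20 × v/6.

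- Yearly arm: 0.20 × (1+2+3+4+5+6)/36 = 11.7%, so 4.56 × 0.117 = 0.5 cancer.
- 3-year arm: 0.20 × (0.5 + 1)/2 = 15.0%, so 22.8 × 0.15 = 3.4 cancers.

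A constant dropout hazard reaching 20% at 6 years gives nearly the same result, 12.0% and 15.3%. At 10% dropout the uniform figures halve. The part of the 3-year-arm loss due to schedule is (0.150 − 0.117) × 22.8 ≈ 0.8 cancer. The rest of the gap between 3.4 and 0.5 arises because more cancers are assumed in that arm.

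**3. If lost patients stay in the denominator as cancer-free** (456 per arm; the share shown is the share of each arm's cancers that goes unrecorded):

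| Lost, yearly / 3-year | Recorded rates | Difference | Power |
|---|---|---|---|
| 0% / 0% | 1.00% v 5.00% | 4.0 points | 0.944 |
| 20% / 20% | 0.80% v 4.00% | 3.2 points | 0.886 |
| 15% / 25% | 0.85% v 3.75% | 2.9 points | 0.833 |
| 25% / 15% | 0.75% v 4.25% | 3.5 points | 0.924 |

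**4. If lost patients are excluded or censored and loss is unrelated to risk.** The expected difference stays at 4.0 points, with power about 0.89 at 20% loss.

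**5. If dropout changes risk.** Suppose the 20% who leave the yearly arm then carry a 5% risk. The true rate in that arm is 0.8 × 1% + 0.2 × 5% = 1.8%, so the true difference is 5.0 − 1.8 = 3.2 points and the ratio 2.8. Excluding lost patients would report 4.0 points and a ratio of 5, which is bias away from no difference.

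**The case against.** Several stronger readings are tempting, and the protocol does not support them.

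- *More loss in the 3-year arm, and so bias toward no difference.* The protocol gives one loss figure for both arms, and six visits rather than two could equally raise dropout in the yearly arm. Shrinkage follows when lost patients count as cancer-free. Steps 4 and 5 give no bias, or bias the other way.
- *A threefold imbalance.* With first endoscopies at 12 and 36 months, equal uniform dropout leaves three times as many 3-year-arm patients never assessed. That counts unassessed patients, not missed cancers. The missed shares are about 15% and 12%, a ratio near 1.3.
- *The second/third wording discards later yearly-arm procedures.* It fits a baseline, 3-year and 6-year schedule, but the bullets that follow apply the section to patients on either interval, and follow-up runs to 6 years. It is loose shorthand.
- *Cancers found outside scheduled visits are certainly unrecorded.* This is inferred from silence. Outcome assignment is not limited to scheduled procedures, nothing says that endoscopies brought forward go unrecorded, the variable list is not shown, and non-attendance is not a stated end of follow-up.

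These points remove any claim about direction. What remains is that the protocol describes no contact with non-attenders, no capture of cancers diagnosed elsewhere and no vital-status check, while it expects losses and answers them only by recruiting more patients.

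**Conclusion.** The point holds as a gap in ascertainment, not as a demonstrated bias in one direction. Capture is described only through follow-up endoscopies and the resection or staging that follows, while the trial is powered on all outcome 2 events at 6 years. The extra 152 patients address precision, not missing events.

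The likely size is modest but not negligible against so few events: about 3 or 4 missed cancers in the 3-year arm and fewer than 1 in the yearly arm. That rests on equal 20% dropout, uniform in time, and even spread of cancers over visits. The difference could fall to 3.2 points, stay at 4.0 or be overstated, depending on dropout by arm, its relation to risk, and the handling of lost patients. The protocol fixes none of these. Because the direction is unknown and cannot be repaired after the event, a cheap improvement in data collection is worth making.

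**What to change.** In *Subsequent clinical evaluation and follow-up* and *End of study*:

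1. State that stopping protocol endoscopy does not end follow-up.
2. At 6 years, ascertain for every randomised patient any gastric cancer diagnosed anywhere (date, and outcome 2.1, 2.2 or 2.3 where available) and vital status, by telephone, hospital records or a registry where accessible.
3. Count these cancers, and those found at unscheduled endoscopies, as outcome 2 in the allocated arm. Since follow-up now ends at the first outcome, say also whether a cancer after outcome 1 counts.
4. As a wording edit only, replace the reference to the second/third procedure with *every follow-up procedure, scheduled or not*.

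The cost is a short amendment and a records or telephone check across 15 centres in nine countries. It covers all 912 patients, but the added work falls mainly on non-attenders, roughly 91 to 182 people at 10% to 20% of 912. No extra endoscopy or biopsy is needed. Registry access will vary, and some cancers found outside the protocol will lack full staging.
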